4.4 Pharmacodynamic Evaluations

Unless otherwise stated, the following pharmacodynamic (PD) variables are evaluated for both Stage 1 and Stage 2. All PD parameters will be defined for each period. The periods under consideration for summary and analyses are run-in (i.e., baseline), each dosing period or treatment period (as applicable), and washout period (i.e., follow-up period).

For Stage 1 stool diaries, the baseline PD parameters will be calculated using all diaries from run-in period; dosing period PD parameters will be calculated on dosing day immediately following each dose (for CSBM and SBM after dose, need to consider the day before dosing for the rescue medications use); and washout PD parameters will be calculated using diaries excluding the first day diaries (i.e., this one day diaries will be attributed to last dosing period).

For Stage 2 stool diaries, all the diaries for each dosing period will be used for the calculation of PD parameters. The washout period started 24 hours of last dose.

For Stage 1 sleep diaries, PD parameters will be calculated using all diaries from run-in period; up to last dosing period. The first 7-day diaries after last dosing period will be attributed to last dosing period and the second 7-day diaries after last dosing period will be attributed to washout period.

For Stage 2 sleep diaries, PD parameters will be calculated using all diaries from run-in period; all diaries in each dosing period up to last dosing period. The washout period started 24 hours of last dose.

4.4.1 Stool Diary Data

Stage 1 Pharmacodynamics Parameters

- Stage 1 complete spontaneous bowel movement (CSBM) is defined as CSBM (Yes) without rescue meds within 24 hours based on dosing day diary.
- Stage 1 spontaneous bowel movements (SBM) is defined as SBM (Yes) without rescue meds within 24 hours based on dosing day diary
- CSBM days per week will be calculated as follows:
 - a. Run-in and washout period: calculation will be based on all diaries in Run-in and Washout period (excluding the first day diary in the period).

$$\text{CSBM Days per Week} = \frac{\text{Sum of days with CSBM without rescue meds within 24 hours}}{\text{Number of Diary Days}} \times 7 \text{ days}$$

- b. Treatment period: calculation will be based on Stage 1 CSBM as:

$$\text{CSBM Days per Week} = \frac{\text{Sum of days with Stage 1 CSBM}}{\text{Number of Dosing Days}} \times 7 \text{ days}$$

- SBM days per week will be calculated as follows:
 - a. Run-in and washout period: calculation will be based on all diaries in Run-in and Washout period (excluding the first day diary in the period).

$$\text{SBM Days per Week} = \frac{\text{Sum of days with SBM without rescue meds within 24 hours}}{\text{Number of Diary Days}} \times 7 \text{ days}$$

- b. Treatment period: calculation will be based on Stage 1 SBM as:

$$\text{SBM Days per Week} = \frac{\text{Sum of days with Stage 1 SBM}}{\text{Number of Dosing Days}} \times 7 \text{ days}$$

- Average ease of passage for each period is defined as
 - a. Run-in and washout period: calculation will be based on all diaries in Run-in and Washout period (excluding the first day diary in the period).
 - b. Treatment period: calculation will be based on diaries on dosing days.

$$\text{Average ease of passage} = \frac{\text{Sum of ease scale w/o rescue meds within 24 hrs}}{\text{Number of BMs w/o rescue meds without 24 hrs}}$$

- Average stool consistency for each period is defined as
 - a. Run-in and washout period: calculation will be based on all diaries in Run-in and Washout period (excluding the first day diary in the period).
 - b. Treatment period: calculation will be based on diaries on dosing days.

$$\text{Average stool consistency} = \frac{\text{Sum of stool consistency w/o rescue meds within 24 hrs}}{\text{Number of BMs w/o rescue meds without 24 hrs}}$$

- Days using rescue med per week for each period is defined as
 - a. Run-in and washout period: calculation will be based on all diaries in Run-in and Washout periods (excluding the first day diary in the period).

$$\text{Days using rescue meds per Week} = \frac{\text{Sum of days using rescue meds}}{\text{Number of Diary Days}} \times 7 \text{ days}$$

- b. Treatment period: calculation will be based on diaries on dosing days.

$$\text{Days using rescue meds per Week} = \frac{\text{Sum of days using rescue meds}}{\text{Number of Dosing Days}} \times 7 \text{ days}$$

These first two parameters will be treated as categorical variables while other parameters will be treated as continuous variables.

Stage 2 Pharmacodynamics Parameters:

- CSBM days per week for each dosing period is defined as:

$$\text{CSBM Days per Week} = \frac{\text{Sum of days with CSBM w/o rescue meds within 24 hours}}{\text{Number of Diary Days}} \times 7 \text{ days}$$

- CSBM episodes per week for each period is defined as:

$$\text{CSBM episodes per Week} = \frac{\text{Sum of daily CSBM episodes w/o rescue meds within 24 hours}}{\text{Number of Diary Days}} \times 7 \text{ days}$$

where daily CSBM episodes = $\begin{cases} \# \text{ of CSBM occurrences w/o rescue meds within 24 hrs for each diary day} \\ 0 \text{ if none CSBM w/o rescue meds within 24 hrs for each diary day} \end{cases}$

- SBM days per week for each dosing period is defined as:

$$\text{SBM Days per Week} = \frac{\text{Sum of Days with SBM w/o rescue meds within 24 hrs}}{\text{Number of Diary Days}} \times 7 \text{ days}$$

- SBM episodes per week for each period is defined as:

$$\text{SBM episodes per Week} = \frac{\text{Sum of Daily SBM Episodes w/o rescue meds within 24 hrs}}{\text{Number of Diary Days}} \times 7 \text{ days}$$

where Daily SBM Episodes

$$= \begin{cases} \# \text{of SBM occurrences without rescue meds with 24 hours for each day diary} \\ 0 \text{ if none SBM without rescue meds for each day diary} \end{cases}$$

- Average ease of passage for each period is defined as

$$\text{Average ease of passage} = \frac{\text{Sum of ease scale w/o rescue meds within 24 hrs}}{\text{Number of BMs w/o rescue meds without 24 hrs}}$$

- Average stool consistency for each period is defined as

$$\text{Average stool consistency} = \frac{\text{Sum of stool consistency w/o rescue meds within 24 hrs}}{\text{Number of BMs w/o rescue meds within 24 hrs}}$$

- Days using rescue meds (i.e., laxative/suppository/enema) per week for each period is defined as

$$\text{Days using rescue meds} = \frac{\text{Sum of Days with daily rescue meds use}}{\text{Number of diary days}} \times 7 \text{ days}$$

- Rescue med episodes per week for each period is defined as

$$\text{Rescue med episodes per week} = \frac{\text{Sum of daily rescue meds use}}{\text{Number of diary days}} \times 7 \text{ days}$$

$$\text{where daily rescue meds use} = \begin{cases} \# \text{of episodes of rescue meds use for each diary day} \\ 0 \text{ if no rescue meds use for each diary day} \end{cases}$$

All of the above parameters are treated as continuous variables.

- Success (Yes/No) based on CSBM days will be defined as “Yes” if either one criteria is met:
 - if increase of one or more in CSBM days per week compared to baseline
 - 3 or more of CSBM with CSBM per week

Success based on CSBM will be treated as categorical variable and is primary endpoint.

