3 STUDY DESCRIPTION

The study will consist of 7 periods. Total duration will be 21-29 weeks (maximum treatment period for each individual is 4-8 weeks).

	STAGE 1		STAGE 2A				
Period 1	Period 2.1	Period 2.2	Period 3.1	1 Period 3.2 Period 4		Period 5	
Run-in sentinel group (Cohort 1)	Single dose escalation sentinel group	Washout	Run-in (Cohort 2)	Identification of prokinetic dose using a 10 subject sentinel group followed by the remaining subjects	1:1 Randomization onto placebo or prokinetic dose	Washout	
2 weeks	3 weeks	2 weeks	2 weeks	≤17days	6 days	2 weeks	
N=10	N=10	N=10	N=40	N=40	N=40	N=40	

3.1 **Periods**

PERIOD 1 (Stage 1):

Run-in period for Sentinel Group (n=10)

Duration: 2 weeks

Conducted at home with 1 visit to the clinical trial facility and a telephone call at day 14

Patients who meet the inclusion/exclusion criteria and who sign an informed consent will be enrolled in the study. The sequence of patients entering the study will be used to generate the patient identifying number for the conduct of the study (e.g., all case report forms, laboratory assessments). At the beginning of the run-in period, patients will be asked to stop benzodiazepines and other sedatives, hypnotics, opiates, proton pump inhibitors. Patients will remain off these medications throughout the study. They will be allowed to continue antihistamines, anticholinergies, anti-psychotics, dopamine, and anti-depressant medication at stable doses. Use of laxatives and suppositories will be documented in the stool diary. Laxatives, softeners, Dulcolax suppositories and enemas will be disallowed during the 24-hour period before the start of the treatment period. They will keep daily diaries and record stool frequency, consistency, ease of evacuation and use of suppositories, laxatives, softeners, fiber, chia or flax seeds, as well as a sleep diary and record various sleep parameters. At the end of the Period, they will be re-evaluated using the daily stool chart to assess the severity of constipation. A stool occurring within 24 hours of laxative, stool softener, bulking agent or suppository use will not be counted. Only spontaneous stools will be counted. A spontaneous stool is a stool occurring in the absence of a laxative, stool softener, bulking agent or suppository.

Exploratory Sleep Assessment:

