Participants will receive a phone call and be asked about adverse events. They will also provide their daily stool chart to assess the severity of the constipation and use of laxatives, softeners, bulking agents and suppositories. *Patients with two or fewer complete, spontaneous bowel movements will qualify for the treatment period. A bowel movement occurring within 24 hours of suppository, softener, bulking agent or enema use will NOT be counted. A spontaneous stool is a stool occurring in the absence of a laxative, softener, bulking agent or suppository.* PAC-SYM and PAC-QOL to be administrated on day 14, or at the clinic at Dose 1 visit the following day if they fail to bring the completed survey.

PERIOD 2.1 (Stage 1): Single dose

Safety, tolerability and pharmacokinetics of orally administered single-dose ENT-01 in Sentinel Group

Duration: 22-57 days

The 10 patients in the sentinel group will be assigned to Cohort 1 and will participate in 8 single dosing periods.

Subjects	D1	D4-8	D7-15	D10-22	D13-29	D16-36	D19-43	D22-50	D25-57
1-2	25mg	50mg	75mg	100mg	125mg	150mg	175mg	200mg	
3-4		25mg	50mg	75mg	100mg	125mg	150mg	175mg	200mg
5-6		25mg	50mg	75mg	100mg	125mg	150mg	175mg	200mg
7-8		25mg	50mg	75mg	100mg	125mg	150mg	175mg	200mg
9-10		25mg	50mg	75mg	100mg	125mg	150mg	175mg	200mg

All 10 patients will be pre-selected in advance of check-in for their first scheduled dosing period. All laxatives, suppositories, softeners, bulking agents and enemas will be disallowed during the 24-hour period before or after the administration of study medication. Patients will wear the I-Button continuously for the entire dosing period. The first two patients (subjects 1-2) will first be admitted and given a single dose. The study will be conducted at a hospital-based clinical unit and patients will be monitored for 24 hours after the dose. Unless there are any safety

concerns, patients will be released at this time and brought back for the next dosing on Day 4-8 (D4-8), after a minimum of a 72 hour observation period. Dopamine will be taken prior to the clinic visit on an empty stomach. Patients will self-administer the study medication during their clinic visit. The dose will be taken on an empty stomach along with 8 oz. of water after baseline observations in the clinic. The patient will not be allowed to ingest any food for at least 60 minutes after study medication.

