4.6 Concomitant Medication

- Preventive laxatives will be discontinued during the run-in period. Throughout the study,
 patients will be allowed to take constipation *rescue medication on demand*, and only if
 they have not had a bowel movement in three consecutive days.
- In stage 1, rescue medication (laxative, bulking agent, softener, suppository) can be taken as needed and as stated above, and noted in the stool chart. Rescue medication cannot be taken during the 24 hrs before or after study medication. Any bowel movement produced within 24 hours of rescue medication will not be counted.

In Stage 2, rescue medication (Dulcolax suppository and/or enema) can be taken on demand during the run-in period as stated above and noted in the stool diary. During the dosing period, rescue medication is taken on the evening of the third dose at any given level if a stool has not been produced in response to three days of study medication. Enterin CMO should be consulted for any questions related to rescue medication. Rescue medications will be recorded in the daily diary. Bowel movement produced within 24 hours of rescue medication will not be counted as either spontaneous bowel movement or complete spontaneous bowel movement.

- In both stages, protein pump inhibitors will be discontinued during the run-in period and reinstated during the wash-out period.
- Benzodiazepines, hypnotics, other sedatives, barbiturates, and opiates will not be allowed.
 All medications shall be reviewed and dis/approved by the investigator on a case-by-case basis.
- Selective serotonin reuptake inhibitor (SSRI), SNRI, tricyclic antidepressants anticholinergics, anti-histamines and anti-psychotics are permissible at stable doses.
- Dopamine agonists and amantadine will be allowed if on a stable dose for at least 4 weeks preceding the study.
- Deep brain stimulation is allowed at the PI's discretion.

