7.7.1 Analysis of Continuous Pharmacodynamics Data

The following continuous PD parameters and their change from baseline will be summarized by period (run-in [baseline], dosing periods (diary) or treatment period (questionnaire data), and washout) for each appropriate population, using descriptive statistics as specified in Section 7.1 (General Statistical Procedures).

Stool Diary PD parameters:

- CSBM days per week
- CSBM episodes per week (Stage 2 only)
- SBM days per week
- SBM episodes per week (Stage 2 only)
- Average ease of passage
- Average stool consistency
- Days using rescue meds per week
- Number of rescue meds use per week

Sleep Diary PD parameters:

- Total sleep time (hours) per day
- Delay (minutes) in sleep onset per night
- Total awake time (hours) per night
- Number of wakes per night
- Number of arm or leg thrashing days per week

Questionnaire PD parameters:

- Total score from NMSQ
- Total score from BDI-II
- Total score from MMSE
- Total score from UM-PDHQ
- Total scores from PFS-16
- Total score and 3 subdomain scores from PAC-SYM
- Total Score and 4 subdomain scores from PAC-QoL
- Total Score from RBDQ
- Total score and Part I to III scores from UPDRS

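### Stage 1 stool and rescue rates per week are dosing-day proportions multiplied by 7, and their change from run-in does not compare like with like

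*SAP*

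**What the plan says.** Protocol 3.1 (Period 2.1) states that each Stage 1 patient "will participate in 8 single dosing periods", one dose in each, with return visits "after a minimum of a 72 hour observation period". SAP 4.4 takes stool data for these periods from one diary day: "dosing period PD parameters will be calculated on dosing day immediately following each dose".

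SAP 4.4.1 defines the treatment-period CSBM rate with numerator "Sum of days with Stage 1 CSBM" and denominator "Number of Dosing Days", multiplied by 7. SBM days and days of rescue use follow the same pattern. In run-in and washout the denominator is diary days. SAP 7.7.1 has these variables and their change from baseline "summarized by period (run-in [baseline], dosing periods (diary) or treatment period (questionnaire data), and washout".

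Two protocol rules on rescue matter here. In run-in: "A stool occurring within 24 hours of laxative, stool softener, bulking agent or suppository use will not be counted". Around dosing (Protocol 4.6, and likewise 3.1): "Rescue medication cannot be taken during the 24 hrs before or after study medication".

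**The concern.** A reader of the Stage 1 tables will take CSBM days per week to be a bowel frequency that patients had. It is not. It is the share of dosing days with a CSBM, put on a weekly scale as if the patient had been dosed daily. The days between doses are left out, although diaries are kept on them.

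The change from baseline then subtracts a run-in rate built on all diary days, under different rescue conditions. A fall in rescue use, or part of a rise in CSBM or SBM, could come from how the two periods are counted and not from the drug. Stage 2 uses the same variable name for a rate over all diary days, so the two stages would report different quantities under one label.

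**Working it through.** The documents give no numerical result for these variables, so there is no plan figure to reproduce. The formulas can be evaluated directly.

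**Inputs**
- Dosing days: 1 per dose level, 8 per patient if all doses are given (Protocol 3.1; SAP 4.4).
- Patients: 10.
- Days in Period 2.1, from the Protocol 3.1 dosing table. Subjects 1-2 run from D1 to D22-50, which is 22 to 50 days. Subjects 3-10 start on D4-8 and end on D25-57: 25 - 4 + 1 = 22 and 57 - 8 + 1 = 50 days.

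**1. One dose level.** 7 x 0/1 = 0 or 7 x 1/1 = 7, with nothing between. The mean over 10 patients is 7 times the responder proportion and moves in steps of 7/10 = 0.7.

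**2. Pooled over 8 doses.** 7k/8 for k = 0 to 8: 0, 0.875, 1.75, 2.625, 3.5, 4.375, 5.25, 6.125, 7.

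**3. Which level applies.** SAP 4.4.1 labels the formula as the treatment period, which suggests pooling. SAP 4.4 allows dosing period or treatment period as applicable. SAP 7.7 gives by-dose summaries only if judged necessary, while 7.7.1 names dosing periods for diary data. The level is not fixed.

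**4. Size of the extrapolation.** Assume CSBMs on 4 of 8 dosing days and none on other days.
- SAP formula: 4/8 x 7 = 3.5 per week.
- All days, shortest schedule: 4/22 x 7 = 1.27 per week.
- All days, longest schedule: 4/50 x 7 = 0.56 per week.
- Overstatement: 22/8 = 2.75-fold to 50/8 = 6.25-fold.

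**5. Rescue days.** Rescue is barred for 24 h before and after each dose, so the dosing-day count is about 0 apart from deviations. If run-in use is r days per week, the reported change is 0 - r = -r whatever the drug does. For example, an assumed r = 1 gives -1 per week. Rescue taken between doses is not seen by this variable.

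**6. CSBM and SBM against run-in.** Let p be the daily CSBM probability with no drug effect, and f the share of run-in days inside a rescue window. Assume CSBMs are equally likely inside and outside those windows.
- Expected dosing-day rate: 7p.
- Expected run-in rate: 7p(1 - f), because the stool is removed and its day stays in the denominator.
- Expected apparent gain: 7pf.

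The documents give neither p nor f. For assumed 7p of 1 to 2 per week and f of 1/7 to 4/7, the gain runs from 1 x 1/7 = 0.14 to 2 x 4/7 = 1.14 per week. With f = 0 it is zero.

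**The case against.** The strongest defence is that using the dosing day alone is a stated choice that suits single doses, since days between doses may involve rescue. Multiplying by 7 does not bias the mean over dosed days and loses no information. The SAP also tabulates dosing-day CSBM and SBM as Yes/No (4.4.1 and 7.7.2), so the natural summary is already planned. If the formula is read as pooled, nine values are possible and not two. All of this stands. It does not make the weekly label correct or the change from baseline comparable.

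Three stronger readings are tempting, and the documents do not support them.
- A reader might infer that the CSBM change will be positive without any drug effect. That depends on run-in laxative use, which is unknown. Without such use the expected change is zero. At a single dose level most unaffected patients would show a fall: at a true rate of 1 per week, about 6 of 7 dosing days give 0.
- A reader might infer that these rates choose the STDE, the starting dose for Stage 2. Protocol 3.1 and 9.20 require a prokinetic effect in at least some patients, but nothing says it is read from the weekly rate.
- A reader might take 57 days as one patient's exposure. It is a calendar day counted from the first dose of subjects 1-2; no patient's own schedule exceeds 50 days.

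**Conclusion.** The point holds. The Stage 1 treatment-period weekly rates are rescaled dosing-day proportions: 0 or 7 at one dose level, 7k/8 when pooled, with the level unstated. In the worked example, which assumes no CSBM between doses, the reported rate is 2.75 to 6.25 times the rate over the patient's actual days.

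The comparison with run-in is not like for like. For rescue days this follows from the protocol's own bar on rescue around dosing and needs no assumption beyond adherence to it. For CSBM and SBM the direction follows from the counting rule whenever run-in stools are discounted, but the size is unknown. It turns on run-in laxative use, where the protocol is unclear. Section 3.1 (Period 1) has laxative use recorded in the diary and disallows it only in the 24 h before treatment starts. Section 4.6 stops preventive laxatives in run-in and limits rescue to cases with no bowel movement for three days. These passages must be reconciled.

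The SAP text is wrong as written, but the consequence is minor. Stage 1 pharmacodynamics are exploratory (SAP 3.1.3) and only described, and the Success test belongs to Stage 2.

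**What to change.** For Stage 1, report the proportion of dosing days with a CSBM and with an SBM, by dose, using the Yes/No variables already defined. Delete the treatment-period weekly rates for CSBM, SBM and rescue days, and their changes from baseline.

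If a weekly stool or rescue rate is still wanted, compute it from all Period 2.1 diary days and handle rescue-window days identically in run-in, Period 2.1 and washout: either out of both numerator and denominator throughout, or kept throughout. Removing them from run-in alone would reverse the asymmetry, because rescue is also allowed between doses.

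The cost is SAP wording. No new data are needed and there are fewer derived variables.

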Each dose period will be staggered, so that patients 1-2 will be administered a single dose of the drug at the lowest dose of 25mg. Once 24 hours have elapsed, and provided there are no safety concerns, they will be sent home and brought back on day 4-8 for the next dose. During the days the patients are home, they will complete the daily diaries and e-mail them to the study coordinators. The study coordinators will call the patients every other day starting on the day following discharge for each dose and determine with the patient if a suppository or laxative is needed, as well as inquiring about any adverse events. Diary information will also be discussed with the patients during the telephone calls. Patients 3-10 will be dosed after the first two patients have been observed for 72 hours, i.e. on Day 4. Patients 1-2 will also be brought back on Day 4-8 and will be given a single dose of 50mg. Once another 24 hours have elapsed and provided there are no safety concerns, they will all be sent home and instructed to return on Day 7 for the next dosing level. This single dosing regimen will be continued until each patient has been given a single dose of 200mg or has reached a dose limiting toxicity (DLT). DLT will be the dose which induces repeated vomiting, diarrhea, abdominal pain or symptomatic postural hypotension within 24 hours of dosing. Maximum tolerated dose (MTD) will be the highest dose for which there was no more than 1 DLT endpoint (refer to Section 9.8, DLT endpoint criteria). A review of safety, tolerability and adverse events will occur prior to administration of each dose level and at the end of Period 2 with DSMB. After the last dose of medication, BDI, MMSE, Trail-making A and B, NMSQ, UM-PDHQ, PFS-16, RBDQ, PDSS, PAC-SYM and PAC-QOL will be administered.

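### Stage 1 on-treatment rescue use is counted only on days when rescue is banned, so it is zero for every adherent patient whatever ENT-01 does

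*SAP*

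**What the plan says.** SAP section 4.4 sets the general rule for Stage 1 stool diaries: "dosing period PD parameters will be calculated on dosing day immediately following each dose". Section 4.4.1 applies it to rescue use. The treatment-period value is the number of days with rescue divided by the number of dosing days, times 7, with the instruction "Treatment period: calculation will be based on diaries on dosing days". For the two comparison periods the same section says "calculation will be based on all diaries in Run-in and Washout periods (excluding the first day diary in the period", so run-in and washout use every diary day but the first.

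SAP section 7.7.1 lists "Days using rescue meds per week" among the continuous parameters summarised by period together with change from baseline.

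The protocol restricts rescue around each Stage 1 dose. Section 3.1, Period 2.1, states: "All laxatives, suppositories, softeners, bulking agents and enemas will be disallowed during the 24-hour period before or after the administration of study medication". Section 4.6 repeats it: "Rescue medication cannot be taken during the 24 hrs before or after study medication". Between doses rescue is available. Patients are at home, and the coordinator telephones every other day to "determine with the patient if a suppository or laxative is needed". Section 4.6 also allows Stage 1 rescue as needed, on condition that three consecutive days have passed without a bowel movement.

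**The concern.** The days on which the SAP counts rescue are the days on which the protocol forbids it, and the days on which rescue may be taken are left out of both numerator and denominator. The on-treatment figure then records compliance with the ban and says nothing about the need for laxatives.

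The comparison periods do not work this way. The run-in value is unlikely to be zero, because patients qualify by needing a laxative or softener at least weekly (Protocol section 3.1, Period 1), and Stage 1 run-in bars laxatives only in its last 24 hours. In the second washout week patients restart their original medications. If those include laxatives, and they are recorded as rescue, the table could show use before treatment, none on drug, and use again afterwards. That pattern resembles an on-off drug effect but would come from the rescue rule. Neither SAP section warns of this.

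**Working it through.** The plan gives no expected value, sample size or power for this parameter, so there is no figure of its own to reproduce. The check has four steps.

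**Inputs**
- Eight single doses per patient, 25 to 200 mg (Protocol section 3.1, Period 2.1).
- Doses 3 to 7 days apart, from the dosing table in the same place. The eighth dose falls on Day 22 at the shortest spacing and Day 50 at the longest.
- Ban from 24 h before to 24 h after each dose (Protocol sections 3.1 and 4.6).
- Formula: rescue days on dosing-day diaries / number of dosing days x 7 (SAP section 4.4.1).

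**1. Does the ban cover the whole dosing day?** Take a dose at hour h, with h between 0 and 24. The ban runs from h - 24, which is at or before 0, to h + 24, which is at or after 24. The whole calendar day is covered for any dose time. If the dosing-day diary is read instead as the 24 h after the dose, that also lies inside the ban.

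**2. Value under the SAP formula**
- Adherent patient: 0/8 x 7 = 0 days/week. A patient who stops early has fewer dosing days but the same zero numerator.
- Change from baseline: 0 - run-in value = minus the run-in value.
- One deviation in eight doses: 1/8 x 7 = 0.875 days/week. Two: 2/8 x 7 = 1.75.

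**3. What is left out.** Dosing days are 8 of 22 diary days at 3-day spacing (36%) and 8 of 50 at 7-day spacing (16%). Assume, for illustration, one rescue day in each of the seven gaps between doses.

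| Spacing | Diary days, first to last dose | All-diary rate | SAP rate |
|---|---|---|---|
| 3 days | 22 | 7/22 x 7 = 2.23/week | 0 |
| 7 days | 50 | 7/50 x 7 = 0.98/week | 0 |

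**4. Choice of denominator for a corrected rate.** Assume an illustrative run-in rate of 1.75 rescue days/week and no drug effect, so that total use is unchanged but falls only outside the ban. A gap of T days has (T - 2)/T of its time outside the ban: 1/3 for T = 3 and 5/7 for T = 7.
- Dividing by days outside the ban: 1.75/(1/3) = 5.25/week, a spurious change of +3.50; or 1.75/(5/7) = 2.45/week, a spurious change of +0.70.
- Dividing by all diary days from first to last dose: 1.75/week, a change of 0.

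**The case against.** Several points on the other side stand.

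- The zero is not guaranteed for every patient. A deviation on a dosing day is counted, and the SAP does not assume perfect adherence: section 4.4 tells the analyst to consider rescue on the day before dosing when deriving bowel-movement outcomes.
- SAP section 4.4 assigns the first washout-day diary to the last dosing period. If that is the calendar day after the last dose, use later than 24 h after dosing could be captured once. The text is ambiguous, and one such day does not rescue the measure.
- A dosing-day analysis suits a single-dose design for bowel movements after a dose. It fails only for a behaviour that is barred on that day.
- The consequence is small. Stage 1 has 10 patients, pharmacodynamics is an exploratory objective there (SAP section 3.1.3), the parameter is descriptive and no test is attached. Between-dose use remains visible in the stool diary listings (SAP section 7.9) and the concomitant medication outputs (section 7.5).

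A reader might infer from the dose spacing that rescue is permitted for 33% to 71% of each interval. The documents do not support that. Those figures, (T - 2)/T, are only time outside the 24-hour bans, and section 4.6 adds the condition of three consecutive days without a bowel movement. The share of time in which rescue is actually available cannot be derived from the plan.

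**Conclusion.** The rule is wrong as written, with limited reach. For every patient who follows the protocol, the Stage 1 on-treatment rescue rate is 0 and its change from baseline is minus the run-in value, regardless of drug effect. Any non-zero value reflects non-adherence, apart from the possible extra diary day after the last dose. Run-in and washout are computed on a different set of days, so the periods are not comparable.

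This rests on the ban and the dosing-day rule as stated. The 2.23 and 0.98 days/week, and the 1.75 run-in rate, are illustrations and not figures from the documents.

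Two stronger readings go too far. A reader might infer that all patients will show zero; that holds only for adherent patients. A reader might also infer that the defect touches dose selection or the efficacy conclusion. The Stage 1 dose-finding rule (Protocol section 3.1, Period 2.1) rests on safety, tolerability and prokinetic effect and does not name rescue use. Stage 2 rescue parameters use all diary days, and the primary endpoint is Stage 2 success on complete spontaneous bowel movements.

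**What to change.** In SAP section 4.4.1, compute Stage 1 treatment-period rescue use from all Period 2.1 diary days from first to last dose, divided by the number of those diary days, times 7. Report rescue on dosing days separately, as protocol deviations. Footnote the table to say that rescue was barred around each dose: the ban covers 48 of 72 h (67%) of each gap at 3-day spacing and 48 of 168 h (29%) at 7-day spacing, so even the corrected rate may be held down by the rule.

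Otherwise, drop the treatment-period value and its change from baseline. Do not divide by rescue-permitted days only, because that inflates the rate relative to run-in.

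The cost is SAP wording and programming, plus a rerun of the Stage 1 summary if the analysis described in SAP section 5.2 has already been done. Patients already keep daily diaries between doses, and the all-diary calculation needs only the date of use. No clinical rescue rule changes.
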